6.8.4 Creatinine Clearance

Participants who enroll with a Grade 2 CrCl will discontinue PrEP only if there is an increase in severity (to Grade 3 or 4). If the calculated creatinine clearance is <60 mL/min, it should be confirmed ideally within approximately one week of the receipt of the results. Study drug should be halted temporarily awaiting confirmatory testing. The PSRT should be consulted for further guidance about restarting study drug for participants who fail to have a confirmed test within two weeks of receiving the initial result. If the calculated creatinine clearance is confirmed to be <60 mL/min, the study drug must be temporarily discontinued. The participant will be monitored as deemed clinically necessary in consultation with the PSRT until level returns to baseline (screening value) or stabilizes.

6.9 Expedited Adverse Event (EAE) Reporting to DAIDS

Requirements, definitions, and methods for expedited reporting of adverse events are outlined in Version 2.0 (or latest version) of the DAIDS EAE Manual, which is available on the DAIDS RSC website at <https://rsc.niaid.nih.gov/clinical-research-sites/manual-expedited-reporting-adverse-events-daids>

The DAIDS Adverse Event Reporting System (DAERS), an internet-based reporting system, must be used for EAE reporting to DAIDS. In the event of system outages or technical difficulties, EAEs may be submitted via the DAIDS EAE form. For questions about DAERS, please contact NIAID CRMS Support at [contact]. Site queries may also be sent with the DAERS application itself.

If the site has difficulty accessing the DAERS website, sites will submit EAEs by documenting the information on the current DAIDS EAE form. This form is available on the RSC website: <https://rsc.niaid.nih.gov/clinical-research-sites/manual-expedited-reporting-adverse-events-daids>. For questions about EAE reporting, please contact the RSC at [contact].

6.10 Reporting Requirements for this Study

The study agents for the purposes of SAE/EAE reporting are part of a fixed dose combination tablet of FTC/TDF (also outlined in Section 4).

For each study participant, the SAE/EAE reporting period begins at Enrollment (Day 0) and ends when the participant's follow-up in the study ends (at the Week 9 Visit). All reportable SAEs occurring during the study reporting period will be reported to the principal investigator and for EAEs to the DAIDS RSC Safety Office in an expedited manner, within three reporting days of site awareness of the events (see definition in Appendix D of the DAIDS EAE Manual). After the study has ended, sites must report Suspected Unexpected Serious Adverse Reaction (SUSARs) as defined in Version 2.0 of the DAIDS EAE Manual if the study site becomes aware of the event on a passive basis, i.e., from publicly available information. Site staff will also report information regarding SAEs to their IRB or other local regulatory agencies in accordance with all applicable regulations and local IRB requirements.

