2.5.2 Study design for pregnant cisgender women

This will be an open-label, non-randomized, single-arm, pharmacologic study of daily directly observed therapy. In addition to the cohort of non-pregnant cisgender women describe above, a contemporaneous cohort of up to 18 pregnant cisgender women will be recruited to evaluate the impact of pregnancy on blood and cellular drug benchmark concentrations. Cisgender women must be at 13-26 weeks gestation to give sufficient time for 8 weeks of DOT follow-up. This gestation age was chosen to balance feasibility and risk-benefit and is informed by preliminary work we have done that shows greater reduction in TFV and TFV-DP concentrations in the 2nd and 3rd trimester’s compared to the 1st trimester⁵². We will make all effort to have cisgender women across the entirety of this gestation age spectrum to allow analyses that look across the 2nd and 3rd trimester. To ensure an ethical approach for provision of PrEP in pregnancy (i.e., only exposing PrEP to those who want and might benefit from it) all pregnant cisgender women will be at high risk for HIV and willing to use PrEP. HIV risk and eligibility will be determined according to the Kenya guidelines for PrEP, as described in Table 3. Pregnant cisgender women will receive only daily PrEP dosing (7 doses per week) and matched on age to non-pregnant cisgender women in daily dosing arm. After 8 weeks of DOT PrEP, pregnant cisgender women will be linked to continue PrEP at the clinic of their choice, including at the Thika site clinic itself, permitting seamless access to PrEP and continuation after the study.

Table 3: Kenya national guideline indicators of substantial risk for HIV and indication for PrEP:

Partner of HIV-infected person not on ART or on ART for <6 months
Has >1 partner of unknown status
Engages in transactional sex
History recent STI (past 6 months)
Recurrent PEP use
Inconsistent or no condom use
Injection drug use.

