- At screening, evidence of a viable pregnancy with gestational age of 13-26 weeks after the date of conception with sonographic confirmation. *If adequate sonographic results are not available from medical records at screening, an ultrasound must be performed in the interim so that the result is available at study entry.*
- At elevated risk for acquiring HIV according to Kenya guideline for PrEP. This is to ensure an ethical approach for provision of PrEP in pregnancy (i.e., only exposing PrEP to those who want and might benefit from it). *Kenya national guidelines define substantial risk for HIV and recommend PrEP be an option for individuals reporting partner of HIV-infected person not on ART or on ART for <6 months, >1 partner of unknown status, transactional sex, recent STI, recurrent PEP use, no or inconsistent condom use*
- At study entry, willing to use PrEP during pregnancy for HIV prevention

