At each scheduled pharmacological visit, antenatal records will be reviewed, and assessment of fetal heart tones will be conducted. After 8 weeks of DOT PrEP, pregnant cisgender women will be linked to continue PrEP at the clinic of their choice, including at the Thika site clinic itself, permitting seamless access to PrEP for and continuation for HIV prevention after the study. After 8 weeks of DOT PrEP, if a pregnant cisgender woman chooses not to continue with PrEP for protection against HIV, they may have two additional visits after their last PrEP dose – one visit at week 9 and a second visit within weeks 10 to 16. In the event of pregnancy loss during study follow up, study drug procedures and follow up will be terminated and women will be linked to appropriate clinical standard care including continued access for PrEP. After completing DOT phase of study, pregnant women will have observation visits until end of the study or up to the infant's first birthday (12 months) after delivery whichever occurs first to obtain pregnancy outcomes (i.e., term live birth, preterm birth, birth defects or pregnancy loss) and infant growth outcomes (i.e., weight, head circumference and height). Post DOT maternal/infant visit will 1 (i.e., birth visit), 6, and 12 months. Medical and medication history at birth will be reviewed and will consist of information recorded on medical records at birth as well as information obtained at the Birth Visit (Month 1 post-delivery).

The following should be source documented as part of medical and medications history at the Birth Visit: **Pregnancy/birth outcomes:** Term live birth, preterm birth, birth defects or pregnancy loss, Sex at birth Birth length, weight, and head circumference at birth (obtain from medical records; these measurements will also be performed by study staff at the infant Birth Visit), Apgar scores at one and five minutes (obtained from medical records)

Infant growth outcomes: obtained at 1, 6 and 12 months will include: Length, weight, and head circumference.

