6.6 Serious Adverse Event (SAE)

The Serious Adverse Event (SAE) Reporting Category, as defined in Version 2.0 (or latest version) of the Manual for Expedited Reporting of Adverse Events to DAIDS, will be used for this study. Only SAEs deemed related to the study product must be reported in an expedited fashion to DAIDS.

All SAEs as defined by ICH guidelines regardless of relationship to the study agent(s) will be reported and are as follows:

- Results in death,
- Is life-threatening,
- Requires inpatient hospitalization or prolongation of existing hospitalization,
- Results in persistent or significant disability/incapacity, or
- Is a congenital anomaly/birth defect

Important medical events that may not be immediately life-threatening or result in death or hospitalization but may jeopardize the patient or may require intervention to prevent one of the outcomes listed in the definition above. Such determination may be made through medical or scientific judgment. Examples include the following: intensive treatment in an emergency room or at home for allergic bronchospasm; blood dyscrasias or convulsions that do not result in hospitalization; development of drug dependency or drug abuse; etc.

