7.6 Planned Interim Analyses

Because the study is non-therapeutic and relatively small ($N < 100$) the study team will monitor for safety as described above, but not efficacy. Thus, drug concentration outcomes will not be part of the assessment as samples will be batched tested at the end of the primary data collection. At least one Formal Interim Analysis at 50% enrollment (overall or 50% recruitment for pregnant cohort, whichever occurs first) to review data related to patient safety, including baseline characteristics, creatinine

clearance, HIV infections, and pregnancy outcomes (preterm birth, pregnancy loss, birth defects). The study team will carefully document any adverse events in pregnant cisgender women or infants for careful review.

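### Section 6.10 closes SAE/EAE reporting at the Week 9 visit, but follow-up continues beyond it and nearly all deliveries come later

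*Combined protocol and SAP*

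**What the plan says.** - **Reporting period (6.10).** The "reporting period begins at Enrollment (Day 0") and closes when the participant's "follow-up in the study ends (at the Week 9 Visit"). SAEs in that period go to the principal investigator, and EAEs go to DAIDS within three reporting days of site awareness. The only later rule applies once the study has ended, and covers SUSARs that the site learns of passively from public information.
- **Follow-up, both cohorts (5.2, 5.2.2, Table 5).** Eight weeks of DOT are followed by up to eight weeks of post-DOT sampling: visit 11 in week 9 and visit 12 in weeks 10-16.
- **Follow-up, pregnant women (5.4).** After DOT, "pregnant women will have observation visits until end of the study" or until the infant is 12 months old, whichever is sooner. Maternal/infant visits fall 1, 6 and 12 months after delivery. Their stated purpose is to obtain preterm birth, birth defects, pregnancy loss and infant growth.
- **Women who conceive on study (6.7, 8.5).** They are followed to pregnancy outcome; 8.5 limits this to the end of the study.
- **SAE definition (6.6).** The list includes "Is a congenital anomaly/birth defect". All SAEs are to be reported whatever their relationship to product, but only related ones are expedited to DAIDS.
- **Entry window.** Section 2.5.2: "Cisgender women must be at 13-26 weeks gestation to give sufficient time for 8 weeks of DOT follow-up". Section 3.1: "gestational age of 13-26 weeks after the date of conception with sonographic confirmation".
- **AE ascertainment (5.2, Table 5).** AE assessment runs from entry to week 8, with none listed at visits 11 or 12.

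**The concern.** The sentence in 6.10 gives two end points that cannot both hold. The general rule, end of follow-up, would cover deliveries. The visit named in parentheses would not. A site needs a definite closing visit and will probably apply the named one.

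If it does, the protocol actively observes births and infants for months while stating no SAE/EAE rule for the interval between week 9 and study end. A birth defect is an SAE by the protocol's own list and will usually be recorded at or after delivery, when the stated duty to report has already lapsed. Events in the off-drug weeks 10-16 fall outside the period in the same way.

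**Working it through.** No sample size, power or error rate is involved. The check is a timeline.

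**1. Can week 9 be reproduced as the end of follow-up?** DOT plus post-DOT sampling is 8 + up to 8 = up to 16 weeks. Week 9 is only the first of the two post-DOT visits. For pregnant women, follow-up ends at study end or infant age 12 months. Neither cohort gives week 9.

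**2. Gestation when the period closes.** Gestational age at study week w = entry age + w. Section 2.5.2 gives entry at 13-26 weeks. Section 3.1 counts the same range from conception. Assuming the usual two-week offset (not in the documents), that is 15-28 weeks by last menstrual period. Term is taken as 37-42 weeks, also an assumption.

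| Dating | Entry | Week 9 | Week 16 | Study week reaching 37 wk | Study week reaching 42 wk |
|---|---|---|---|---|---|
| 2.5.2, as stated | 13-26 | 22-35 | 29-42 | 11-24 | 16-29 |
| 3.1, from conception | 15-28 | 24-37 | 31-44 | 9-22 | 14-27 |

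For example, 13 + 9 = 22 and 26 + 9 = 35; 15 + 9 = 24 and 28 + 9 = 37. On the first dating, no participant is at term when reporting closes. On the second, only the latest possible entrant just reaches 37 weeks at that point. Term deliveries fall in study weeks 11-29 or 9-27, and the birth visit follows about a month later.

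**3. Illustrative share of deliveries inside the period.** Assume entry age x is uniform over the window and delivery age is normal with distribution function F. The chance of delivery by week 9 is the average over x of [F(x + 9) - F(x)] / [1 - F(x)]. The cohort size is from 2.5.2 ("a contemporaneous cohort of up to 18 pregnant cisgender women will be recruited").

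| Assumed delivery age, mean (SD), weeks | 2.5.2 dating: chance; expected of 18 | 3.1 dating: chance; expected of 18 |
|---|---|---|
| 39 (2) | 0.13%; 0.02 | 1.29%; 0.23 |
| 39 (2.5) | 0.45%; 0.08 | 2.32%; 0.42 |
| 38.5 (3) | 1.39%; 0.25 | 4.57%; 0.82 |

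The expected number delivering after closure is therefore between 18 - 0.82 = 17.18 and 18 - 0.02 = 17.98 of 18. Of preterm births, about 1%-5% on the first dating, or 8%-15% on the second, would occur by week 9.

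**4. Would week 16 be enough?** Not for pregnant women. They are then at 29-42 or 31-44 weeks, so many would still be undelivered. The period has to follow the maternal/infant visits.

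**5. Does another rule fill the gap?** The SUSAR sentence in 6.10 applies after the study has ended and to passive awareness. The maternal/infant visits are active observation within the study, so it does not cover them.

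**The case against.** The best defence is that the operative rule in 6.10 is the end of follow-up. Read with 5.4, that already includes births, and the parenthesis is a slip. This is a fair reading and a reason to call the point an inconsistency. It does not remove the need to correct the text, because the only visit named is the wrong one.

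Several safeguards also stand:

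- Section 5.4 collects the birth and infant outcomes.
- Section 7.6 has the team document adverse events in pregnant women and infants for review.
- Sections 6.1 and 6.2 provide a safety monitor and PSRT meetings about every six months, or ad hoc.
- Section 6.3 gives participants a 24-hour contact number.
- Section 6.10 keeps SAE reporting to the IRB and local regulators under their own rules.
- Section 6.9 defers to the DAIDS manual, which cannot be consulted here.

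These protect detection and review. None states an SAE/EAE closing date that agrees with 5.4.

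Four stronger readings are tempting, and the documents do not support them:

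- **That no term birth can fall inside the period.** On the 3.1 dating, the latest entrant reaches 37 weeks just as it closes.
- **That every birth defect escapes expedited reporting because of the window.** Unrelated SAEs are not expedited to DAIDS under any window, and a defect detected before week 9 is inside it.
- **That birth outcomes go uncollected.** Section 5.4 schedules their collection.
- **That the interim safety review will have no births to examine.** Its trigger is 50% enrollment ("overall or 50% recruitment for pregnant cohort, whichever occurs first"), so few births are possible. But the documents give no accrual rate, preterm births and losses can come early, and 7.6 provides for at least one such analysis.

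Ending AE assessment at week 8 is also consistent between 5.2 and Table 5. It matters here only because the reporting window should match ascertainment.

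**Conclusion.** Section 6.10 is wrong as written. It contradicts itself, and its Week 9 end point conflicts with 5.2 and 5.4. If the named visit is followed, about 17 to 18 of 18 deliveries come after reporting closes, together with most preterm births and any birth defect first found at or after delivery. Of these outcomes, 6.6 lists birth defects as SAEs; preterm birth appears only as a safety-review item in 7.6.

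The loss is limited to the stated duty to report: to the principal investigator for all SAEs, and to DAIDS within three reporting days for those related to study product. The outcome data themselves are not lost.

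The conclusion rests on the entry window and visit schedule in the protocol. The 37-week definition of term and the two-week dating offset are assumptions that affect only the edge of the range. The percentages depend on assumed delivery distributions and serve as illustration only.

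**What to change.** Reconcile 6.10 with 5.2, 5.4 and 6.6. Replace the Week 9 parenthesis with the participant's last protocol visit, defined as:

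- the week 10-16 visit for non-pregnant women;
- the last maternal/infant visit under 5.4 for pregnant women and their infants;
- the pregnancy outcome for women who conceive on study, in line with 6.7 and 8.5.

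Add AE assessment at visits 11 and 12 in Table 5 and 5.2.2 where those visits occur, and adjust the matching sentence in 5.2. Section 5.4 offers these visits to pregnant women who choose not to continue PrEP, so they will not apply to every pregnant participant.

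The cost is protocol wording, an AE form at two existing visits, and a few more safety reports. No new visit is required. An extra safety review triggered by deliveries is optional and is not part of this correction.

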6.11 Social Impact Reporting

It is possible that participants' involvement in the study could become known to others, and that a social impact may result (i.e., because participants could be perceived as being HIV-infected or at risk or "high risk" for HIV infection). For example, participants could be treated unfairly, or could have problems being accepted by their families and/or communities. A social impact that is reported by the participant and judged by the IRB/designee to be serious or unexpected will be reported to the responsible site's IRBs at least annually, or according to their individual requirements. Social impacts will be collected and reported on CRFs during regular visits. In the event that a participant reports a social impact, every effort will be made by study staff to provide appropriate care and counseling to the participant as necessary, and/or referral to appropriate resources for the safety of the participant. The study site will provide such care and counseling in accordance with standardized guidance in the SSP Manual. While maintaining participant confidentiality, study site may engage their CAB in exploring the social context surrounding instances of social impacts, to minimize the potential occurrence of such an impact.

7 STATISTICAL CONSIDERATIONS

7.1 Review of Study Design

An open-label, randomized, three-arm, directly observed therapy, pharmacologic study. HIV-uninfected non-pregnant cisgender women will be randomly assigned 1:1:1 to 1 of 3 dosing frequencies of DOT TDF/FTC PrEP: 2, 4, or 7 doses/week to help differentiate poor and modest from perfect. An additional contemporaneous cohort of pregnant to receive daily dosing will also be recruited to evaluate the impact of pregnancy on blood and cellular drug levels. We will measure drug concentrations in blood, vaginal fluid, and tissue during the study.

7.2 Study endpoints

Aim 1: Mean, variance, and dose proportionality for TFV-DP in plasma, DBS, and PBMC for 2, 4, 7 of DOT TDF-FTC dosing per week.

Aim 2: Prediction model of adherence rate by level of TFV-DP in DBS.

7.3 Data Analysis

7.3.1 Primary outcomes

Primary outcome 1: The goal is to quantify the effect of dose on steady state TFV-DP in DBS and PBMC based on an incomplete block design. C_{ss} (drug concentration at steady state) will likely require a normalizing log transform, such that geometric means and CIs will be reported. Dose proportionality will be assessed using the power model (on the natural log scale) $\ln(Y_{ijk}) = \mu + S_i + \beta \log(D_k) + \varepsilon_{ijk}$ (Eqn. 1).⁷³ Where Y_{ijk} is the response, C_{ss}, for the kth dose (k=2, 4, and 7 doses per week), ith subject (i=1...54); μ is the overall mean, S_i is a random subject effect, and ε_{ijk} is random error. Dose proportionality dictates that $\beta=1$ for dose-dependent parameters and we will assume dose proportionality if the 90% CI is contained within the limits (0.8, 1.25). We will use the observed week 8 concentrations for the dose-proportionality model. Week 8 is approximately 90% of steady state (3.3×17 -day half-life = 8 weeks). The SAS

mixed procedure will be utilized for model (Eqn 1), again assuming a random subject effect. For the primary analysis, we assume no effect of ‘non-daily dosing’ regimens; although this will be examined in a secondary analysis. If dose proportionality is not shown, we will examine proportionality separately for each of the “non-daily dosing” dosing regimens. If dose proportionality is still not demonstrated when adherence regimens are examined separately, we will consider dose as a categorical predictor. Change in objective function and/or AIC will be used to compare models. This approach will be used to further probe dose proportionality and the final model(s) will be used as a basis for simulation studies. Additionally, we will fit a model with following first-order kinetic equation to the TFV-DP data: $C_t = C_{ss} * (1 - e^{-k*t})$, where C_t is the TFV-DP at time t (i.e., day 4, weeks 1, 2, 3, 4, 5, 6, 7, 8), C_{ss} is the fitted concentration at the steady-state plateau and k is the fitted elimination rate constant, and half-life is $\ln(2)/k$. The fitted C_{ss} will be used in the dose-proportionality model. These approaches use non-compartmental and a simple one-compartment model, respectively. Finally, the percentage of dose can be used as a regressor because the concentration at steady-state is directly proportional to dose frequency and TFV-DP clearance [$C_{ss} = (\text{dose rate})/CL$]. Time post dose does not have to be accounted for because it does not impact the TFV-DP concentration given the 17-day half-life. Importantly, we have used these approaches to assess dose proportionality in two similarly designed studies that have been published. [<https://pubmed.ncbi.nlm.nih.gov/32539288/>].⁷⁴⁻⁷⁸

Primary outcome 2: The goal is to identify TFV-DP cut points associated with adherence levels. For the primary analyses, we will attempt to discriminate adherence for 2, 4 and 7 dosing based upon TFV-DP. As above, we will combine the “non-daily dosing” regimens. Linear mixed models with random intercepts, 25th percentiles, and receiver operating characteristics curves will be used to generate predicted concentration thresholds for varying dosing frequency (ranging from 2 to 7 doses/week) for each matrix-analyte pair. Analyses will be adjusted for age, contraception use, study arm, BMI, eGFR, and hematocrit.

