7.3.2 Secondary outcomes

1. Examine models to predict non-daily adherence based on TFV/FTC and TFV-DP in DBS.

We assume the modeling approaches of Aim-1. We will first consider a saturated model allowing a separate mean for each dose/adherence group. The results will then be compared to a reduced model with a class variable indicating non-daily dosing groups” or 100% dosing (that is, the effect of “non-daily dosing” adherence does not differ by dose groups). Drug concentration predictors of “non-daily dosing” will focus on TFV-DP in relationship to other drug moieties such as FTC-TP and FTC and TFV. For instance, the ratio of TFV-DP to FTC-TP may be used as a predictor of “2” versus “4 dosing per week. A proportional odds logistic approach which allows for an ordinal outcome and extensions which control for correlations between repeated measurements on a subject will be utilized in SAS or R statistical software. In addition, we will employ PK models (see Aim-1) to simulate TFV-DP to FTC-TP ratios for other dose regimens and estimate cut points for predicting non-daily dosing patterns.

2. To quantify the effect of pregnancy on the benchmark concentrations of TFV, TFV-DP, FTC, and FTC-TP in pregnant cisgender women using daily DOT FTC-TDF PrEP.

Using modeling approaches, we will compare the benchmark concentrations of TFV, FTC, TFV-DP, and FTC-TP between pregnant cisgender women using daily DOT FTC-TDF PrEP. Analyses will be stratified by age and pregnancy gestation.

3. Examine relationships among drug concentrations in plasma, RBC, DBS, and PBMC.

We will use mixed and non-linear mixed effects models to determine if concentrations in various matrices are related.

4. Evaluate the influence of demographics, biological) on drug concentrations.

Kruskal-Wallis parametric test will be used to compare demographics and key study variables (e.g., age, pregnancy, mean corpuscular volume and HCT, contraception use, study arm, BMI, eGFR). Secondary analyses are considered hypothesis generating and will not correct for multiple comparisons.

5. Compare drug concentrations in DBS from fingerstick versus transferring blood from blood tubes.

Since these are paired DBS samples, we will compute the ratio of TFV-DP in the two samples and a mixed model on the natural log of the ratio will be utilized to determine if CI is within 0.8 and 1.25, indicating equivalence. Bland-Altman analyses will also be evaluated.

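### The dose-proportionality limits (0.8, 1.25) are placed on the power-model slope without conversion for the 2-to-7 dose range, which leaves an asymmetric margin with a loose upper side and a fallback step with no slope

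*Combined protocol and SAP*

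**What the plan says.** Under Primary outcome 1 in Section 7.3.1, dose proportionality "will be assessed using the power model (on the natural log scale"), that is, log concentration is regressed on log dose with slope beta. The response is indexed "for the kth dose (k=2, 4, and 7 doses per week), ith subject (i=1...54"), and "S_i is a random subject effect". Beta equal to 1 is taken as proportionality, and the rule is "we will assume dose proportionality if the 90% CI is contained within the limits (0.8, 1.25"). The response is the observed week 8 concentration; a second version uses a fitted steady-state concentration.

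The same paragraph calls the analysis "based on an incomplete block design". Section 7.1 describes something else: non-pregnant women "will be randomly assigned 1:1:1 to 1 of 3 dosing frequencies of DOT TDF/FTC PrEP", so each woman has one dosing frequency throughout. Section 7.5 agrees.

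If the rule fails, the plan has two steps. First, "If dose proportionality is not shown, we will examine proportionality separately for each of the" non-daily regimens. If that also fails, dose becomes a categorical predictor, with models compared by objective function or AIC.

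Section 7.3.2, item 5, uses the same pair of numbers for the ratio of fingerstick to tube DBS concentrations, "to determine if CI is within 0.8 and 1.25, indicating equivalence". Section 7.4 sizes the study on the precision of a mean. It gives no probability of meeting the dose-proportionality rule.

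**The concern.** The pair 0.8 and 1.25 is symmetric on the log scale and is a natural margin for a ratio of two means, as in Section 7.3.2, item 5. The slope of a power model is an exponent. What a given slope means for concentrations depends on how wide the dose range is, so a margin on the slope has to be derived from a margin on the ratio and the range actually studied. Section 7.3.1 shows no such step and gives no reason for the limits.

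Dose proportionality is part of primary objective 1, this is the only pass-or-fail rule attached to it, and the plan uses the resulting model as the basis for simulation. A margin wider than it appears would let a departure of clear size be reported as proportional more often than the 5% per side that a 90% interval normally gives. A second worry is that the step after a failed test cannot give a slope as it is worded.

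**Working it through.** **Inputs.** Doses of 2, 4 and 7 per week, so the range is r = 7/2 = 3.5 (Section 7.3.1). Planned arm size 18, and about 16 after 10% non-completion (Section 7.4). Mean 1605 and SD 405 fmol/punch in DBS from US men, so CV = 405/1605 = 25.2% (Section 7.4). SD on the natural log scale = sqrt(ln(1 + 0.252²)) = 0.248. The limits are chosen rather than derived, so there is no figure of the plan's to reproduce. The statement that week 8 is about 90% of steady state does reproduce: 1 − 2^(−56/17) = 0.898. With the same half-life in every arm, this factor cancels from the slope.

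**1. What the limits allow.** The dose-normalised ratio of 7 to 2 doses per week is 3.5^(beta − 1).
- beta = 1.25: 3.5^0.25 = 1.368, 37% above proportionality.
- beta = 0.80: 3.5^(−0.20) = 0.778, 22% below.

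No single dose range turns both limits into 0.8 and 1.25 as ratios. The upper would need r = 1.25^(1/0.25) = 2.44 and the lower r = 0.8^(−1/0.20) = 3.05.

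**2. Converted limits.** For the ratio to stay within 0.8 to 1.25 over a 3.5-fold range, beta must lie within 1 ± ln(1.25)/ln(3.5) = 1 ± 0.178, or 0.822 to 1.178. The lower limit moves by 0.022 and the upper by 0.072.

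**3. Precision of the slope.** Log doses are 0.693, 1.386 and 1.946, with mean 1.342 and squared deviations summing to 0.788. At 18 per arm, SE(beta) = 0.248/sqrt(18 × 0.788) = 0.0659. With t(52) = 1.675, the 90% half-width is 0.110. At the expected SD, an estimate must therefore fall between 0.910 and 1.140 to pass as written, an observed ratio of 0.89 to 1.19.

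**4. Chance of declaring proportionality.** Ordinary regression, normal errors on the log scale, allowing for the estimated SD:

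| CV, women per arm | Limits | True ratio 1 (beta = 1) | True ratio 1.25 (beta = 1.178) | True ratio 0.80 (beta = 0.822) |
|---|---|---|---|---|
| 25.2%, 18 | as written | 89% | 28% | 9% |
| 25.2%, 18 | converted | 69% | 5% | 5% |
| 25.2%, 16 | as written | 85% | 26% | 9% |
| 25.2%, 16 | converted | 61% | 5% | 5% |
| 35% (assumed), 18 | as written | 57% | 19% | 8% |
| 35% (assumed), 18 | converted | 24% | 4% | 4% |

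At a true beta of 1.25 (37% excess) with CV 25.2%, the rule as written passes 5% of the time.

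**5. The fallback.** Within one regimen all women have the same log dose, so the design matrix (intercept and log dose) has rank 1 and no slope exists. If the step instead means each regimen against daily dosing, slopes exist. For 4 versus 7, the sum of squares is 36 × (0.560/2)² = 2.82 and t(34) = 1.691, so the half-width is 1.691 × 0.248/sqrt(2.82) = 0.250. That interval is about 0.50 wide, against limits 0.45 wide, so at the expected SD it cannot fit. For 2 versus 7 the half-width is 0.112.

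**6. The random subject effect.** With one value per woman, the variance of each observation is the sum of the subject and error variances, and only that sum enters the likelihood. The split is not identifiable, but beta and its interval equal those from ordinary regression.

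**The case against.** Several points on the other side stand.

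A reader might infer that a 37% departure would be declared proportional. The documents do not support that: the whole interval, not the estimate, must lie within the limits, and a true 37% excess passes at the nominal 5%. The 37% is how far the interval may reach.

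The looseness is mostly on one side. At a true ratio of 0.80 the rule as written passes 9% of the time, not far from 5%.

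Section 7.3.1 states no ratio criterion. That a 25% margin was meant is an inference from the familiar pair of numbers and from Section 7.3.2, item 5, which is a separate analysis. Nor does the text say in words whose 90% interval it means; beta is the natural reading, because the same sentence sets beta to 1. If a ratio was meant, or a wider slope margin was chosen on purpose, the plan could say so and justify it. What remains is that the margin is unstated in concentration terms and unexplained.

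A reader might also infer that a failed test stops the analysis, or that the random subject effect distorts the result. Neither follows. The later categorical-dose step is estimable in a parallel design, as is the saturated model in Section 7.3.2, item 1, and the subject term leaves beta and its interval unchanged.

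Finally, this rule is not the whole of primary objective 1. Expected concentrations are also reported, with geometric means and intervals, and the adherence cut points of Primary outcome 2 come from other methods.

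**Conclusion.** The concern holds in a limited form. The limits are wrong as written for a slope over a 3.5-fold dose range: they correspond to ratio limits of 0.778 and 1.368, and the upper one is materially loose. At CV 25.2% and 18 per arm, a true 25% excess passes about 28% of the time rather than 5%, and a true 20% shortfall about 9%. The first fallback step is not estimable if read literally and, for 4 versus 7, not passable at the expected SD if read as a comparison with daily dosing. The incomplete-block label and the subject effect are wording faults with no numerical effect.

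These figures assume log-normal concentrations, the same log-scale SD in all three arms, one value per woman, and a CV taken from DBS in US men on daily dosing. The plan gives no CV for PBMCs, the other primary matrix, or for Kenyan women; the 35% row is an assumption to show the range.

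**What to change.** In Section 7.3.1:

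1. State that the 90% interval is for beta and set its limits to 1 ± ln(1.25)/ln(3.5), that is, 0.822 to 1.178. Comparing the 90% interval of 3.5^(beta − 1) with 0.8 to 1.25 is the same rule.
2. In Section 7.4, report the chance of passing when beta = 1: about 69% at 18 per arm and 61% at 16 per arm for CV 25.2%, and about 24% at 18 per arm for an assumed CV of 35%.
3. Replace the separate examination of each non-daily regimen by dose-normalised geometric mean ratios (2 v 7, 4 v 7, 2 v 4) with 90% intervals from the categorical-dose model already planned. Report them as descriptive estimates, not as a second test: requiring all three to lie within 0.8 to 1.25 would succeed only about 44% of the time under exact proportionality at CV 25.2% and 18 per arm.
4. Drop the incomplete-block wording and the subject effect from the analysis with one value per woman, and fit ordinary regression of log concentration on log dose (52 residual df with 54 women).

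This changes wording only; no visit, sample or participant is added. The price is a rule that is harder to pass: at beta = 1 the as-written chances are 89%, 85% and 57% in the three settings of item 2. If the converted rule is not met, the estimate of beta and the ratios in item 3 still describe how far the data are from proportionality.
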